### **Biochemical markers of infection and protein energy malnutrition**

CRP and ACT (acute phase proteins) will be measured at *screening* (550 children), *baseline* (45 children participating in the RDR test) and at *endpoint* (180 children) as indicators of acute phase response due to infection. In addition, prealbumin will be measured as an indicator of protein nutritional status as these may effect the biochemical indicators of vitamin A and iron status. Serum prealbumin < 10-40 mg/dL is considered as an indicator for protein energy malnutrition. CRP > 5 mg/L and ACT > 0.4 g/L indicate underlying inflammatory disease. Blood analyses will be carried out at Nutritional Biochemistry Laboratory, ICDDR,B, which has extensive in-house and external quality control system.

### **Parasitic infestation**

Parasitic infestation will be measured from stool collected from the screened children (n=550) before the 1st deworming. The intensity of infestation (eggs per gram) will be assessed for helminths (*Ascaris lumbricoides* and *Trichuris trichuria*) and hookworms. Protozoa cysts (*Entamoeba histolytica*, *Giardia intestinalis* and other protozoa cysts) will be verified (as zero, few, moderate or heavy). The data will be used for the assessment of infestation and relationships between outcome parameters.

The faecal samples will be examined microscopically by the quantitative ether sedimentation technique (Hall, 1981). Stool samples will be analysed at the Parasitology Laboratory at ICDDR,B.

### **Confounding factors**

Since the outcome of the intervention study may be affected by factors other than the fish consumed, the confounding variables markers of infection and protein energy malnutrition as well as anthropometry, food intake, morbidity as described below will be measured during study and adjusted for in the statistical analysis.

### **Anthropometry**

Age, sex, height, weight and upper arm circumference (MUAC) will be recorded in the selection of potential subject. Height, weight and MUAC will be measured at *screening* (550 children), at *baseline* (180 children) and at *endpoint* (180 children).

Anthropometry will be measured with the following accuracy: Height will be measured to the nearest 2 mm (using a stadiometer), weight to the nearest 0.1 kg (using an electronic scale) and MUAC to the nearest 1 mm (using MUAC strips). Inter-, intra- individual and instrument variability will be determined before the study.

Changes in weight, height and MUAC will be calculated as well as weight for age, weight for height and height for age. The anthropometric measurements will be compared with the standard values of the National Center for Health Statistics and expressed as Z-scores (NCHS, 1976).

### **Food intake**

One 24 h dietary recall of all 550 children will be conducted as baseline information in order to assess habitual food and nutrient intakes at the group level. In addition, a semi-quantitative dietary assessment of vitamin A intake will be done in order to assess the risk of inadequate dietary vitamin A intake at the group level.

During the feeding trial, between *baseline* and *endpoint*, intakes of nutrients (vitamin A as well as energy, carbohydrate, protein, fat, iron, zinc and calcium) from foods not provided in the test meals will be calculated from biweekly food consumption surveys of the 180 children, using the 24 h recall method.

The results will be used to calculate the total daily intakes of nutrients in each treatment group during the feeding trial based on the following:

1) data from the food consumption surveys conducted between *baseline* and *endpoint* (mean of 4-5 dietary recalls) and 2) the amount of food given in the dishes (corrected for leftovers) and from the chemical analyses of duplicate samples of the dishes (please see below).

The total daily intakes of nutrients during feeding trial will be compared between treatment groups as well as with habitual food and nutrient intake.

The conduction of the 24 h recall method will be based on the method described by Gibson, 1990. The questionnaire is enclosed as Appendix 5.

The method used for conducting the semi-quantitative dietary assessment of vitamin A intake will be based on the method proposed by the International Vitamin A Consultative Group (IVACG) (Underwood *et al*, 1989). The questionnaire is enclosed as Appendix 4.

The health assistants will be trained, the questionnaires will be pre-tested, the health assistants will be checked in the field by supervisors and the filled out questionnaires will be checked daily.

A random check of 5% of the total number will be conducted in order to test the reliability of the 24 h dietary recalls, semi-quantitative assessment of vitamin A intake and morbidity questionnaires. This means that another person repeats the visit in the same household on the same day for 5% of the households. A quick comparison of the field assistant's questionnaire and the supervisor's questionnaire is done on the same day. At *baseline*, the field system may be adjusted to correct the faults.

Socio-economic data, semi-quantitative questionnaire on vitamin A intake, 24 h dietary recall and morbidity data will be conducted by the 9 health assistants and 2 supervisors.

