### **Compliance**

The children and their families will be carefully informed about the importance of eating all of the test meals, not changing their normal diet as well as not taking any nutrient supplements and deworming medication between *screening* and *baseline* as well as during the feeding trial. A physician will be available for any health problems of the children.

Good rapport between the community leaders, parents and ICDDR, B will ensure compliance. Regular visits of study staff to the households as well as daily contact with the children and mothers when consuming the test meals will be used to motivate the children and their families as well as reinforce the messages regarding compliance. During biweekly visits to the households, for collection of morbidity and food intake data the mothers will be asked if their children have been taking nutrient supplements and/or deworming medication.

During previous studies, we have found compliance of follow up was nearly 90%. Child who will eat 80% of the assigned meal will be considered as successful compliance. In this study, we expect atleast 80% compliance to come to feeding at the subcentre although according to sample size calculation if 37 children would complete 6X9 meals would be enough to test the hypothesis of this efficacy trial. In case of drop out, we may carry out stratified analysis for less number of intake.

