End January 2002 - mid February	
Collection of baseline information of the households and the screened children (n≈ 550):
 
 
- socio-economic data
 
- habitual food and nutrient intake (one 24 h recall interview per child)
 
- risk of dietary vitamin A deficiency (one interview per child)
 
- morbidity data (incidence within the last 30 days, one per child)
 
- data entry
 
 
➤ Training of staff for cooking and feeding
 
Continued on the next page!

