**I would like to talk now specifically about what you ate yesterday.**

- 8. Did you eat the normal amount of food yesterday?
  - Yes, same as usual..... 1 (Go to 9)
  - No, more than usual ..... 2
  - No, less than usual..... 3
  - Don't know ..... 9 (Go to 9)

8a. Why didn't you eat the normal amount of food? **[MORE ANSWERS POSSIBLE]**

\_\_\_\_\_

\_\_\_\_\_

\_\_\_\_\_

9. Now I would like you to remember exactly what you did and what foods you ate and any drinks you drunk yesterday. We will start with the first thing you did when you woke up yesterday. What time did you first eat something after you woke up yesterday?  
 What did you eat? **[PROBE FOR MAIN INGREDIENTS OF BHAJJIS, CURRIES, COMPOSITE DISHES]** When did you eat after that? etc. **[PROBE FOR SNACKS BETWEEN MEALS, PROBE FOR DRINKS (TEA WITH/WITHOUT MILK AND SUGAR, ALCOHOLIC DRINKS)]** **PROBE FOR BINP NUTRITION SUPPLEMENT AND ASK FOR FRACTIONS CONSUMED!!!**

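### The before-after comparison of total daily intake mixes a change of measurement method for lunch with any real change in diet

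*Protocol*

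**What the plan says.** All of this is in the protocol.

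- **Habitual intake.** The Food intake section states: "One 24 h dietary recall of all 550 children will be conducted as baseline information in order to assess habitual food and nutrient intakes". The purpose is group-level description. The Time schedule also gives one recall per child. The recall form covers the whole previous day: "Now I would like you to remember exactly what you did and what foods you ate and any drinks you drunk yesterday".
- **Intake during feeding (Food intake).** This is a sum of two parts. The first is intake "from foods not provided in the test meals will be calculated from biweekly food consumption surveys of the 180 children", taken as the mean of 4-5 recalls. The second is the lunch, from "the amount of food given in the dishes (corrected for leftovers) and from the chemical analyses of duplicate samples of the dishes". The section on test meal preparation and distribution confirms that dishes and leftovers are weighed, and gives the serving time as 1300-1400 h.
- **Planned comparison.** The same section continues: "The total daily intakes of nutrients during feeding trial will be compared between treatment groups as well as with habitual food and nutrient intake". Appendix 12, item 1.2.1 (the investigators' responses to the funder's comments), states the same intention to compare with habitual intake.

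**The concern.** Before feeding, lunch is known only from the respondent's memory. During feeding it is weighed and assayed. Home foods stay on recall throughout. For the lunch part of the day, instrument and period are therefore completely confounded: any systematic recall error affects lunch before feeding and not after. No section puts the two periods on a common method or warns about the difference.

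At stake is how the before-after contrast is read. The test meal replaces a home meal, and the Compliance section tells families to keep to "not changing their normal diet as well as not taking any nutrient supplements". A reader will naturally use the contrast with habitual intake to judge how the total diet moved once feeding began. Part of that movement would come from the change of method.

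**Working it through.** The protocol gives no figure for this comparison, so there is none to reproduce. The check asks what the change of method alone would produce.

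**Inputs**
- Lunch share of daily intake, s: about one third. Appendix 12, item 1.4.6, says the child eats one test meal and two meals at home. Equal meals are an assumption; a share of 0.50 is shown as an upper case.
- Recall error, b (recall reports 1 + b of the truth): not in the documents. Assumed -20% to +20%, the same for all meals.
- Weighed and assayed lunch: assumed unbiased.
- True daily intake: set to 1 and unchanged.

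**Formulas**
- Before = 1 + b
- During = (1 + b)(1 - s) + s
- Spurious difference = During - Before = -b × s
- Relative to the recorded habitual value = -b × s / (1 + b)

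**Results at s = 0.33**

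| b | Before | During | Apparent change |
|---|---|---|---|
| -0.10 | 0.900 | 0.933 | +3.7% |
| -0.20 | 0.800 | 0.866 | +8.2% |
| +0.10 | 1.100 | 1.067 | -3.0% |
| +0.20 | 1.200 | 1.134 | -5.5% |

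At s = 0.50 the same errors give +5.6%, +12.5%, -4.5% and -8.3%.

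**Number of recalls.** Setting one recall against a mean of 4-5 does not shift the mean, but it changes the spread. With r the ratio of within-child to between-child variance and k the number of recalls, the SD ratio is sqrt((1 + r/k)/(1 + r)). For r from 1 to 4 (assumed) and k = 4 or 5 it is 0.60 to 0.79. Spreads, and proportions of children below a cut-off, are therefore not comparable between periods either.

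**Comparison between arms.** During feeding all three arms are measured in the same way, so this artefact does not enter the contrast between them.

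**The case against.** The strongest reply is that little depends on this comparison. No hypothesis or specific objective asks about change from habitual intake. The Data Analysis section uses nutrient intake during the study as a covariate, not the change from habitual. Serum retinol, its sample size and the contrast between arms are untouched. All of that stands, and it makes this a secondary, descriptive matter.

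The group-level defence of a single recall (Food intake; Appendix 12, item 1.4.5) answers precision only. Averaging over many children does not remove a systematic difference between two instruments.

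Three stronger readings might be inferred, and the documents do not support them:

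- **A bias of 11-25%.** With 10-20% under-reporting, lunch alone would appear to rise by 1/0.9 = 1.11 to 1/0.8 = 1.25. The planned comparison is of total intake, where the effect is about a third of that, and over-reporting would reverse the sign.
- **550 children compared with 180.** The baseline recall covers all screened children, but the protocol does not say which of them enter the comparison. The 180 are a subset with their own baseline recalls, and the choice may be left to the analysis plan.
- **A fall in home foods would be hidden.** The Food intake section calculates intake from foods not provided as a separate quantity before lunch is added, so it can be reported on its own.

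There are also fair limits on the remedy. The protocol says one home meal is replaced without naming it. Leaving out the midday meal assumes that it is the one displaced, which the 1300-1400 h serving time makes reasonable but not certain. Keeping only recalls of attended feeding days selects on behaviour after randomisation, so it should not be the main analysis.

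**Conclusion.** The point holds as a limited one. The protocol commits to a before-after comparison in which lunch changes instrument when feeding starts, so the difference partly reflects method. With 10-20% under-reporting and a one-third lunch share, the artefact is an apparent rise of about 4-8% in total intake; with 10-20% over-reporting it is an apparent fall of about 3-6%. These figures rest on an assumed recall error common to all meals, an assumed lunch share and an unbiased assay, so the documents establish neither direction nor size. The finding gives no ground for doubting the serum retinol analysis, the covariate model or the intake comparison between arms. It justifies a change of wording to one secondary comparison.

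**What to change.** In the Food intake section:

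1. In the 180 enrolled children, base the before-after comparison on recalled foods other than the midday meal in both periods. The recall form has a column for the hour of eating, so the baseline midday meal can be identified.
2. Repeat this using only recalls that refer to a feeding day the child attended, as a sensitivity analysis.
3. Report the weighed and assayed test meal separately.
4. Keep total intake for the comparison between arms. If total intake is also set against habitual intake, label that contrast descriptive and name the change of method.

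The cost is wording and a small amount of analysis on data already planned. The contrast of total with habitual intake loses prominence. The change does not remove the calendar gap in the Time schedule: the baseline recall runs from end January to mid February, and feeding from mid March to mid May. Some of any remaining difference could be seasonal.

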### **Nutrient analysis of dishes**

For the nutrient analysis of dishes, duplicate samples will be taken in labelled plastic boxes and stored frozen. One sample each of cooked rice (n=5) and vegetable curry (n=5) will be taken biweekly. For the three fish dishes, one sample each will be taken every week (n=9), in total 27. The duplicate samples will be used for chemical analyses of dry matter, vitamin A, energy, protein, fat, iron, calcium and zinc.

### **Morbidity**

The incidence of infection: diarrhoea, dysentery, upper acute respiratory infection, pneumonia, fever, measles, night blindness, vomiting, ear and eye infections, within the last 30 days will be recorded once per screened child, in connection with the collection of *baseline* information (550 children) (Appendix 6). The data will be used for the assessment and relationships between outcome parameters.

For the children (n=180) enrolled in the feeding trial, morbidity (incidence within the last 2 weeks) will be registered biweekly between *baseline* and *endpoint*. The results will be used to calculate mean morbidity (based on 4-5 registrations) in each intervention group during the feeding trial.

Below are description of common morbidity:

URI	Presence of cough and or nasal discharge
ALRI (Pneumonia)	Presence of cough and tachypnoea (>40 resp/min) with or without chest indrawing
Diarrhoea	3 or more loose stools in 24 hours
Dysentery	Loose stools with blood or blood with mucus
Fever	>38 0c body temp.

### **Compliance**

The children and their families will be carefully informed about the importance of eating all of the test meals, not changing their normal diet as well as not taking any nutrient supplements and deworming medication between *screening* and *baseline* as well as during the feeding trial. A physician will be available for any health problems of the children.

Good rapport between the community leaders, parents and ICDDR, B will ensure compliance. Regular visits of study staff to the households as well as daily contact with the children and mothers when consuming the test meals will be used to motivate the children and their families as well as reinforce the messages regarding compliance. During biweekly visits to the households, for collection of morbidity and food intake data the mothers will be asked if their children have been taking nutrient supplements and/or deworming medication.

During previous studies, we have found compliance of follow up was nearly 90%. Child who will eat 80% of the assigned meal will be considered as successful compliance. In this study, we expect atleast 80% compliance to come to feeding at the subcentre although according to sample size calculation if 37 children would complete 6X9 meals would be enough to test the hypothesis of this efficacy trial. In case of drop out, we may carry out stratified analysis for less number of intake.

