Preformed vitamin A, which is found in foods of animal origin, is more efficiently absorbed than most carotenoids and more effective in improving vitamin A status (National Research Council, 1989). However, these foods are considered as not being easily available to and affordable for poor households. Within food based strategies, there has been no focus on the role that small fish can play in preventing and combating micronutrient deficiencies. Small fish is a commonly consumed food in many developing countries and are easily available, relatively cheap and well liked by most household members, including children. In Bangladesh, small fish rank third with respect to amount of raw food intake after rice and vegetables in many communities for large parts of the year ([name] *et al*, 1997). Some commonly consumed small fish species have been found to have extremely high contents of preformed vitamin A (Roos, 2001). For example, mola contains 2,400 - 3,000 RE/100 g raw edible fish (Roos, 2001), 5 times higher than the green leafy vegetable, amaranth (*Amaranthus gengeticuss*) (Varming, 1996). Few other indigenous small fish species in Bangladesh have been identified to have very high contents of vitamin A, chanda (*Parambassis baculis*) (> 1500 RE/100 g raw edible fish); dhela (*Osteobrama cotio cotio*) and darkina (*Esomus danricus*) (500-1,500 RE/100 g raw edible fish) while several other species have been found to have medium contents of vitamin A (100-500 RE/100 g raw edible fish) (Roos, 2001). However, the bioavailability of vitamin A from these small fish still needs to be established. An intake of 45 g mola/d (2,400 RE/100 g raw edible fish) meets the full daily vitamin A recommended dietary allowance of 4-6 years old children (500 RE/d) (National Research Council, 1989), taking a cooking loss of about 50 % into consideration. A pilot trial has shown that children can easily consume 45 g of fish (given as 60 g of fish curry) and even higher amounts, 70 g of fish (given as 90 g of fish curry) from a single main meal (own observations). No study has looked at the efficacy of a daily amount of vitamin A rich small fish on the vitamin A status in humans.

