### Test meals

A pilot study was conducted in the Mirpur slum in October 2000 to develop and test the recipes to be used in the study as well as the procedures and the logistics, in terms of physical set up and manpower of carrying out the study. The dishes developed were cooked and served to 20 children for 5 days. Based on their feedback, adjustments were made. Samples of raw mola and rui and the corresponding cooked fish curries were taken to determine cooking loss of vitamin A. Samples of the cooked vegetable curries were also taken for determination of vitamin A.

The test meals in the different intervention groups have been designed in such a way that they appear and taste as similar as possible. The test meals will consist of rice, a fish curry and a vegetable curry. All foods given in the test meals other than mola are non/low vitamin A rich foods. Rice will be given *ad libitum* in order to adjust for the differences in energy needs due to different ages. Subsequently, all children are given the same fixed amount of rice, the few children who ask for more will be given more. The fish curry to be used in the intervention groups will differ only with respect to the fish species either small fish, mola or big fish, rui. The other ingredients of the fish curry will be onion, garlic, ginger, turmeric, chilli seed, iodised salt and soybean oil. The amount of cooked fish curry used in the intervention groups is fixed to correspond to either 45 g raw cleaned mola or rui/child/meal. The cooked mola curry will be homogenised (blended) so that the vitamin A in mola is uniformly distributed throughout the whole amount. The rui curry will also be homogenised. It was observed that the two fish curries differed in colour, the mola curry being dark green and the rui curry had a yellow tinge. The same vegetable curry will be used in all intervention groups during the study and will be served in a fixed amount. The vegetable curry will consist of bottle gourd in addition to potato, cucumber, onion, mug dal, garlic, ginger, turmeric, chilli seeds, iodised salt and soybean oil.

The recipe for 200 children are shown in appendix 14. However, we shall offer cooked rice 400g, vegetables 200g and blended fish (mola/rui) curry 90 g.

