In the positive intervention group, retinyl palmitate solution will be added to the meal of each child at serving. In order to ensure that the vitamin A recommended intake is met in the vitamin A rich and positive control groups, the daily test meal will contain approximately 500 RE/d.

Mola (300 kg) and rui (1100 kg) will be caught over a period of 4-6 months (starting at the end of 2001 and completing in the beginning of 2002). The fish will be cleaned, packed, weighed in daily portions and stored frozen at the Mymensingh Aquaculture Extension Project until transport to Mirpur. The rice (2400 kg) will be purchased from the Bangladesh Rice Research Institute. The vegetables (6500 kg) will be supplied by a local wholesale vendor.

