### Test meal preparation and distribution

The test meals will be prepared at a centrally located building in the Mirpur slum. The building, which will be rented for 6 months, will be used to conduct the health examination of the children, blood drawing, food storage and cleaning, cooking and feeding of test meals to 180 children. Four head cooks, 24 local kitchen helpers and 7 research assistants will be in charge of preparing and distributing the meals.

The head cooks will be in charge of cooking all dishes, while the local kitchen helpers are needed, especially for the peeling, cleaning and cutting of the vegetables. On a daily basis, four dishes (rice, mola fish curry, rui fish curry and vegetable curry) will be prepared; approximately 130 kg boiled rice, 70 kg vegetable curry, 10 kg mola curry and 15 kg rui curry. In addition, the local kitchen helpers will help in bringing the children to the building, make the children feel welcome, prepare them for eating (for example seeing that they wash their hands), arrange them in intervention groups, and in preparation for receiving the different test meals. They will also assist with meal distribution, encourage and motivate the children to eat the test meal, especially all of the fish curry. In order to ensure that the children eat all the fish curry served, they will first be served the fish curry along with the rice and after finishing the fish curry, they will be served the vegetable curry. The test meals will be served at lunchtime (1300 - 1400 h).

The research assistants will be responsible for instructing and overview the kitchen helpers, supervising that the amounts and procedures described in the recipes are followed by the cooks, weigh the amounts of raw foods to be cooked in each dish, weigh the dishes and serve the test meals. Rice, vegetable curry and fish curry will be weighed and served separately to each child in disposable plastic containers. Disposable plastic containers will be used for hygienic purposes, ease of weighing separate portions as well as ease of administration. Drinking water will be given *ad libitum*. The containers will be marked with the child's identification number. Leftovers of each dish will be weighed to calculate total intake.

We shall have 3 floors of a building to accommodate 3 groups of children.

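### Compliance is set at 80% of the assigned meal, not of the fish curry, so children who ate the full vitamin A dose can be counted as non-compliant

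*Protocol*

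**What the plan says.** The Compliance section of the Protocol gives one rule: "Child who will eat 80% of the assigned meal will be considered as successful compliance". The next sentences concern attendance at the feeding centre and completion of 6 x 9 meals. They do not say whether the 80% refers to weight, to energy or to the number of meals.

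The Test meals section gives the portions: "we shall offer cooked rice 400g, vegetables 200g and blended fish (mola/rui) curry 90 g". It locates the vitamin A of the mola arm in one dish: "All foods given in the test meals other than mola are non/low vitamin A rich foods". For the positive control it says: "In the positive intervention group, retinyl palmitate solution will be added to the meal of each child at serving".

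The section on test meal preparation and distribution sets the serving order: "they will first be served the fish curry along with the rice and after finishing the fish curry, they will be served the vegetable curry". It also provides the measurement: "Leftovers of each dish will be weighed to calculate total intake". Attendance and leftovers are recorded daily, and each of the three fish dishes is sampled weekly for vitamin A assay. The Food intake section calculates nutrient intake from food served, corrected for leftovers, and from those assays. Data Analysis lists nutrient intake during the study as a covariate.

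**The concern.** This is an efficacy trial of a vitamin A dose carried by one small dish. A compliance rule should therefore track how much of that dish was eaten. The stated rule counts the whole meal, most of which is rice and vegetables with little or no vitamin A. It can then label a child by appetite for rice rather than by exposure.

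What is at stake is the reported compliance figure and the argument built on it. The later addendum on vitamin A2 reports preliminary serum retinol in the mola group of 0.59 before and 0.60 µmol/L after, against 0.59 and 0.84 in the positive control. It also states that enough mola was fed. A whole-meal percentage is weak support for such a statement. A percentage based on the fish curry would support it directly.

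**Working it through.** The Protocol gives no worked figure for this rule, so there is none to reproduce. The inputs are the 80% threshold (Compliance), the portions (Test meals), the serving order (Test meal preparation and distribution) and the pilot rice amounts of 200 to 450 g (Preliminary Observations).

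**Reading 1: 80% by weight**

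- Meal: 400 + 200 + 90 = 690 g. Threshold: 0.80 x 690 = 552 g.
- Shares: rice 400/690 = 58.0%; vegetables 200/690 = 29.0%; fish curry 90/690 = 13.0%.
- All fish and all vegetables: 90 + 200 = 290 g, so the rice needed to pass is 552 - 290 = 262 g.
- The same child with 200 g of rice: (90 + 200 + 200)/690 = 490/690 = 71.0%. Full dose, non-compliant.
- All fish and all rice, no vegetables: (90 + 400)/690 = 71.0%. Full dose, non-compliant.
- No fish, serving order kept: no vegetables are served, so at the fixed portion the maximum is 400/690 = 58.0%. Non-compliant, as it should be. Passing on rice alone would take 552 g, above the pilot maximum of 450 g.
- Fish only partly eaten, serving order kept: the child has less than 90 g of fish and no vegetables, so needs more than 552 - 90 = 462 g of rice. That also exceeds the 400 g portion and the pilot maximum.

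At the fixed portions and with the serving order kept, the error therefore runs one way. A child who passes has finished the fish, but a child who fails may have finished it too.

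**Sensitivity to the curry portion**

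The Background section reports that "children can easily consume 45 g of fish (given as 60 g of fish curry", and pairs 90 g of curry with 70 g of fish. Test meals pairs the served curry with 45 g of raw fish but offers 90 g. With 60 g of curry:

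- Meal 660 g, threshold 528 g, fish share 60/660 = 9.1%.
- All fish and vegetables: rice needed 528 - 260 = 268 g. With 200 g of rice, 460/660 = 69.7%.
- No fish, serving order kept: at most 400/660 = 60.6%.

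The conclusion does not depend on which portion applies.

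**Reading 2: 80% of scheduled meals**

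- 6 x 9 = 54 meals; 0.80 x 54 = 43.2, so 44 meals are needed. This counts attendance and says nothing about how much curry was eaten at each meal.

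**The rule placed on the fish curry**

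- Assigned: 54 x 90 = 4,860 g. Threshold: 0.80 x 4,860 = 3,888 g, an average of 72 g per scheduled meal.
- At about 500 RE per meal, and assuming the vitamin A is evenly spread through the blended curry, 80% is about 400 RE per scheduled meal.

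**The case against.** A reader might infer that a child who eats no fish can count as compliant, since rice and vegetables alone make 600/690 = 87.0% of the meal (600/660 = 90.9% with 60 g of curry). The documents do not support this. Vegetables come only after the fish curry is finished, so a fish refuser is capped at about 58%. The zero-dose case needs the serving order to be broken, or about 552 g of rice to be eaten.

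A reader might also infer that the dose eaten will be unknown. It will not be: leftovers are weighed by dish, attendance is recorded, the fish dishes are assayed, and leftover-corrected intake enters the analysis. Nor does the rule distort a planned stratification. The only one mentioned is optional, arises in case of drop-out, and is by number of intakes. No exclusion, analysis set or primary test refers to the 80% label.

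It is tempting to add that the youngest children would be misclassified most. The Protocol says energy needs differ with age, but gives no intake by age. The pilot children were 4 to 11 years old, and 200 to 450 g describes what was offered and eaten on different days, so the frequency of the 200 g case is unknown.

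Finally, the positive-control dose may already belong to the fish dish. The overall aim describes rui with added retinyl palmitate, the ethics abstract says two of the fish dishes contain vitamin A, and three fish dishes are sampled although only two curries are cooked. These passages point to the curry, but the operative instruction says only the meal.

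What stands is narrower: the rule names no dish or unit, and on either reading it does not measure the dose.

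**Conclusion.** The concern holds in limited form. By weight, the compliance rule is 87% rice and vegetables, and it fails children who ate the whole dose-carrying dish: 71% for full fish and vegetables with half the rice, and 71% for full fish and rice without vegetables. By meals attended, it measures attendance only.

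The weight result rests on the stated portions and on reading the 80% as a share of weight, which the text permits but does not say. How many children would be misclassified cannot be estimated from the Protocol. The consequence is a compliance figure that poorly supports interpretation of the mola arm. The primary comparison and the sample size are unaffected. The change is worth making because it costs almost nothing.

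**What to change.** 1. Replace the sentence in Compliance with a definition on the fish curry: cumulative weighed fish curry eaten, divided by fish curry assigned over all 54 scheduled meals, with an absent child counted as zero. Keep the 80% threshold on that quantity. Attendance can be reported separately.
2. Report RE received per child, from the weighed curry intake and the vitamin A assays already planned.
3. Reconcile the Test meals instruction that retinyl palmitate is added to the meal with the overall aim, the ethics abstract and the dish-sampling text, which describe a fish dish with added vitamin A. It must be clear whether curry leftovers measure the dose in the positive control.
4. Reconcile the curry portions in Background and Test meals (60 g or 90 g of curry against 45 g of fish), because the assigned amount is the denominator of the new measure.

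The cost is a few sentences. Leftovers, attendance and assays are already collected. The compliance figure may come out less favourable, because absences then count against it.
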